8.2. Setting

The study will enroll patients according to the eligibility criteria in participating countries across Europe. The recruiting centers will be representative of each country involved in terms of care management systems, of size and of practices (at least when performing feasibility).

Any patient who meets the eligibility criteria will be invited to participate in the study with no selection by the investigators. The enrollment visit will be performed at the time of the patients' inclusion, after the patients' acceptation of enrollment in the study.

Data will come from medical records and will be collected in routine clinical practice. The enrollment visit will comprise a first section on patients' eligibility for every patient whatever pool they belong to and a second section depending on the treatment started (SU or AXI) at the inclusion.

For patients enrolled in the study when AXI is started as a 2^{nd} line therapy, a retrospective section will be completed at patients' inclusion, to collect data on SU 1^{st} line treatment.

For patients who start AXI when SU is discontinued during the study, the AXI initiation visit will resume baseline data that need to be updated.

Follow-up will be ensured during visits in the context of usual patients' care management (non-interventional study). No visits will be required by the protocol of the study. As long as the

patients are treated with SU or AXI, every visit to the center will be recorded. In accordance with ESMO guidelines and physicians clinical practice is real life, follow-up visits are approximately expected:

- during SU treatment: every 6 weeks (every cycle) with tumor assessment approximately every 3 months with respect to the clinical practice
- during AXI treatment: every 4 weeks (every cycle) with tumor approximately assessment every 2 months with respect to the clinical practice

[figure not shown]
When patients come off SU treatment (i.e. are not receiving AXI) or come off Axitinib (after receiving the SU-AXI sequence) they will be followed up every 6 months (separate form) for survival until the end of the study.

Because of the inclusion criteria (Patients being treated with SU in 1st line according to the European approved therapeutic indication and/or being treated with AXI in 2nd line according to the European approved therapeutic indication (except post cytokines)), the medication is prescribed within the regular practice of the physician. Because of the non-interventional nature of the study, there will be no specific requirements with regards to the treatment process. The physician will determine dosage and duration of the treatment, guided by the SmPC and according to his assessment of the individual therapeutic needs of the patient.

The QoL questionnaire will be completed at baseline and then every month for patients receiving AXI. QoL will also be measured at the discontinuation of AXI treatment. Patients will complete the QoL questionnaire at their homes once per month and return it using pre-stamped envelopes. If not done before, the questionnaire will be completed at the site preferentially prior to the follow-up visit(s).

If QoL objective is locally non-compliant with a non-interventional study design, patients will be exempted from performing the questionnaires.

Figure 2 : visit scheme

8.2.1. Inclusion criteria

Patients must meet all of the following inclusion criteria to be eligible for the study:

- Histologically confirmed diagnosis of advanced/metastatic renal carcinoma (clear cell RCC as well as non-clear cell RCC) with measurable disease according to RECIST 1.1
- Patient 18 years of age and over
- Patients being treated with SU in 1st line according to the European therapeutic indication and/or being treated with AXI in 2nd line according to the European approved therapeutic indication (except post cytokines)
- Evidence of a personally signed and dated informed consent document indicating that the
 patient (or a legally acceptable representative) has been informed of all pertinent aspects of
 the study.

8.2.2. Non inclusion criteria

Patients meeting any of the following criteria will not be included in the study:

- 5. Patients being treated with cytokines or any other treatment outside of SU in 1st line
- 6. Patients receiving anti -tumor treatment beyond a second line
- 7. Patients already under Sunitinib, already under Axitinib: enrolment must occur at the beginning of each line of treatment (before or at the first follow up visit)

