8.1. Study design

8.1.1. Global design

ADONIS is an international (EU), prospective (partly retrospective), non-interventional, non-controlled, observational multicenter study.

Patients can be enrolled from several EU countries including Austria, Belgium, Denmark, France, Finland, Germany, Greece, Ireland, Italy, Norway, Portugal, Spain, Sweden, Switzerland, The Netherlands and UK (non-exhaustive list).

Investigators will be specialists in charge of adv/mRCC. The sites involved (at least when performing feasibility) will be representative of their respective country in terms of practice. Participating physicians will not be influenced in their decision making and routine proceedings in any way.

The study will enroll approximately 750 adv/mRCC patients at the 1st and 2nd line treatment level. Patients will be enrolled when they start a treatment with SU in 1st line or AXI in 2nd line post SU treatment.

Patients enrolled at SU initiation, will be followed-up whatever the post SU 2nd line treatment is (AXI, other drugs, no further active treatment, (supportive care)). The possible 1st and 2nd line sequences of treatment under investigation (i.e. patient pools) are (Figure 1):

- SU (prospective) AXI
- SU (retrospective) AXI
- SU not further active treatment (supportive care)
- SU other second line treatment (sorafenib, pazopanib, everolimus, temsirolimus, other)

[figure not shown]
The study will include a retrospective and/or prospective data collection period:

- Retrospective data, consisting of SU 1st line treatment records, will be collected for patients who start the study with AXI in 2nd line.
- Prospective data in terms of medical treatment records, will be collected for all 2nd line AXI patients.

Prospective data will also be collected for all patients enrolled in the study at the SU 1st line level, irrespective of 2nd line treatment, or no further active treatment.

The inclusion period of eligible patients is planned for 54 months, with a minimum 2-year follow-up period. Patients will be followed-up from their enrollment to the end of the study follow up period.

Figure 1: study flow chart

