This sample size of 125 SU-AXI patients in the prospective group will also allow for comparisons with the AXIS-trial with respect to PFS and to demonstrate that the AXI PFS is no worse than 25% of the PFS measured by investigators in the AXIS study (i.e. at least 4.9 months

based on AXIS PFS of 6.5 months when assessed by investigators [2] (80% power, Brookmeyer-Crowley type test, One-sided alpha level (Type I error rate) set at 0.1).

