For each patient, the safety event reporting period begins at the time of the patient's first dose of Sunitinib and/or Axitinib or the time of the patient's informed consent if s/he is already exposed to Sunitinib and/or Axitinib, and lasts through the end of the observation period of the study, which must include at least 28 calendar days following the last administration of a drug under study, a report must be submitted to Pfizer Safety (or its designated representative) for any of the types of safety events listed in the table above occurring during this period. If the investigator becomes aware of a SAE occurring at any time after completion of the study and s/he considers the SAE to be related to Sunitinib and/or Axitinib, the SAE also must be reported to Pfizer Safety.

Causality assessment

The investigator is required to assess and record the causal relationship. For all AEs, sufficient information should be obtained by the investigator to determine the causality of each adverse event. For AEs with a causal relationship to *Sunitinib and/or Axitinib*, follow-up by the investigator is required until the event and/or its sequelae resolve or stabilize at a level acceptable to the investigator, and Pfizer concurs with that assessment.

An investigator's causality assessment is the determination of whether there exists a reasonable possibility that *Sunitinib and/or Axitinib* caused or contributed to an adverse event. If the investigator's final determination of causality is "unknown" and s/he cannot determine whether *Sunitinib and/or Axitinib* caused the event, the safety event must be reported within 24 hours.

If the investigator cannot determine the etiology of the event but s/he determines that Sunitinib and/or Axitinib did not cause the event, this should be clearly documented on the eCRF of the study and the NIS AEM Report Form.

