2. ENROLLMENT

Inc	Clusion Date / / 20 (DD/MM/YYYY) Patier	nt ident	ifier ചച							
Inc	Inclusion criteria									
1.	Histologically confirmed diagnosis of advanced/metastatic renal carcinoma (clear cell RCC cell RCC) with measurable disease according to RECIST 1.1	as well as □ Yes	non-clear □ No							
2. 3.	Patient 18 years of age and over Patients being treated with SU in 1 st line according to the European approved therapeutic inc treated with AXI in 2 nd line according to the European/ approved therapeutic indication exceptes		_							
4.	Evidence of a personally signed and dated informed consent document indicating that the paraceptable representative) has been informed of all pertinent aspects of the study	atient (or a □ Yes	legally							
	date signed// (DD/MM/YYYY)									
	"If one of these boxes is ticked "No", the patient must not be included in the st	tudy"								
No	on-inclusion criteria									
5. 6.	Patients being treated with cytokines or any other treatment outside of Sunitinib in first line Patients receiving anti –tumor treatment beyond a second line	☐ Yes	□ No							
7.	Patients already under Sunitinib, already under Axitinib: enrollment must occur at the beginn treatment (before or at first follow up visit) "If one of these boxes is ticked "Yes", the patient must not be included in the s	☐ Yes	□ No							
Afte	er review all criteria above, is the patient included in the study?	□ Yes	□ No							
	If Yes, date of inclusion// 20 (DD/MM/YYYY)									
	If Not, why?									
P	atient's Demographic data									
Yea	ar of birth (YYYY) Body height cm									
Sex	k □ male □ female Body weight □□□,□ kg									
Ti	ne patient is included in the study with:									
	□ SUNITINIB in first line □ AXITINIB in second line									
	If SUNITINIB is started, please go to the SUNITINIB section and complete the SUN	NITINIB ini	tiation visit							
	If AXITINIB is started, please go to the AXITINIB section and complete the AXITINIB initiation visit									

Axitinib, Inlyta®
A4061078 NON-INTERVENTIONAL STUDY PROTOCOL
ADONIS Amended V12.2
05 December 2014

ADONIS CRF

Subject ID:

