6 ENDPOINTS AND COVARIATES

6.1 EFFICACY/EFFECTIVENESS ENDPOINT(S)

6.1.1 Primary Endpoints

- Progression Free Survival (PFS) under Axitinib in 2nd line post Sunitinib

The PFS will be defined as the time from when the patient receives the first dose of AXI to the time of progression or death due to any cause, whichever occurs first.

PFS status and PFS time will be calculated as detailed below:

Variable name	Definition
PFS status	Patient will not be censored for the PFS analysis (PFS status = 1) in the following cases:
	 Tumor Assessment showing PD in at least one Axitinib follow-up visit (cf. CRF page 29)
	 Death within 3 months after treatment discontinuation / last Tumor Assessment. Death could be reported whether on Axitinib discontinuation page (cf. CRF page 35) or on Study Discontinuation visit (cf. CRF page 37)
	In all other cases, patient will be censored for the PFS analysis (PFS status $= 0$).
	Note: the following cases should be discussed at time of DRMs:
	- Patients with a PD not documented through a Tumor Assessment
	- Patients with no regular Tumor Assessments (i.e. not every 3/4 months)
PFS time	The time to disease progression will be calculated in months as:
(months)	 (Date of first Tumor Assessment showing PD in at least one Axitinib follow-up visit - Start date of Axitinib + 1) / 30.44, if case n°1 described above is reported
	 (Date of death - Start date of Axitinib + 1) / 30.44, if case n°2 described above is reported
	Else, the time to disease progression will be censored as follows:

Variable name	Definition
	 (Date of Axitinib discontinuation - Start date of Axitinib + 1) / 30.44 if patient discontinued Axitinib for any reason other than PD
	 (Date of last follow-up visit - Start date of Axitinib + 1) / 30.44 if patient is lost to follow-up or still under Axitinib
	Note; this could be adapted if necessary (to be discussed at time of DRMs)
	Note:
	- Start date of Axitinib will be the one reported at time of Axitinib initiation visit (cf. CRF page 25 "Therapy started with Axitinib in 2nd line on")
	- Axitinib discontinuation date will be the Date of progression/intolerability or death reported at time of Axitinib discontinuation (cf. CRF page 35)

- Progression Free Survival (PFS) for the sequence Sunitinib-Axitinib

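### Enrolment is permitted up to the first axitinib follow-up visit while the axitinib clock starts at first dose, so the pooled axitinib-line PFS and TTF medians may be overstated

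*Protocol*

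**What the plan says.** **When a patient may enter.** The third non-inclusion criterion (Protocol 8.2.2, numbered 7) bars patients already on treatment but adds that "enrolment must occur at the beginning of each line of treatment (before or at the first follow up visit". Protocol 8.2 expects visits "during AXI treatment: every 4 weeks (every cycle"), and Protocol 8.4 forbids arranging an appointment for the study, so the first visit can fall later than 4 weeks. Protocol 10.1 (reporting period) starts safety reporting at first dose "or the time of the patient's informed consent if s/he is already exposed to Sunitinib and/or Axitinib", so consent after exposure is foreseen. Protocol 8.1.1 describes the usual case: "Patients will be enrolled when they start a treatment with SU in 1st line or AXI in 2nd line post SU treatment".

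**When the clock starts.** SAP 6.1.1 counts axitinib PFS as "the time from when the patient receives the first dose of AXI to the time of progression or death due to any cause". Axitinib TTF has the same starting point.

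**How the data are analysed.** SAP 8.1.2 specifies ordinary Kaplan-Meier and Cox models, and SAP 7 treats incomplete follow-up only as right-censoring. SAP 8.2.2 estimates the primary endpoints in the whole SU-AXI subgroup. Only baseline characteristics are split by point of enrolment (SAP 8.2.5 and 8.2.6). Neither document mentions delayed entry or a sensitivity analysis by enrolment timing, and Protocol 8.9 does not list late entry as a limitation.

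**What is recorded.** The CRF enrolment page has the field "If Yes, date of inclusion".

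**The concern.** A patient who consents at the first follow-up visit has, by construction, not died before it. Because the inclusion criteria require current treatment, that patient has not stopped axitinib either. A similar patient who failed in week 2 cannot be enrolled at that visit. The Kaplan-Meier risk set still counts the late enroller as at risk from first dose, so it includes event-free time that could not have been otherwise. This is left truncation, and right-censoring does not address it.

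Any resulting bias is upward and does not shrink with sample size. It would fall on the pooled axitinib PFS and TTF medians, two of the four primary results.

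**Working it through.** **Plan's own figures.** Protocol 8.5, Table 2: 1.96 × √(0.25/350) = 0.0524, the stated 5.2%. Pool sizes: 525 × 0.68 × 0.35 = 125 patients enrolled at sunitinib start, plus 225 enrolled at axitinib start, gives 350. Only the 225 can enter axitinib late. The 125 are already under observation at their first axitinib dose. The exposed share is at most 225/350 = 0.643.

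**Other inputs.** The true median is m = 6.5 months, the investigator-assessed AXIS figure after sunitinib (Protocol 6), or 4.8 months, the independent-review figure there. The delay L for a 4-week visit is 28/30.44 = 0.92 months.

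**Assumptions not in the documents.** The fraction f of the axitinib pool that enrols late (25–100%), the early hazard, and delays of 2 or 8 weeks as alternatives.

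**Formula.** Let q = f × 225/350 be the share of analysed patients who enter at L. For t > L, Kaplan-Meier from first dose estimates (1 − q)S(t) + qS(t)/S(L). With exponential S, setting this to 0.5 gives

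reported median = m + m × log2[1 + q(1/S(L) − 1)].

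**Worked case (m = 6.5, 4 weeks, f = 100%).** S(L) = 0.5^(0.92/6.5) = 0.907, so 9.3% fail before the visit. Then 1 + 0.643 × (1/0.907 − 1) = 1.066, log2(1.066) = 0.0925, and 6.5 × 0.0925 = 0.60. The reported median is 7.10 months.

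Excess in the pooled median, months, m = 6.5:

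| Delay | f = 25% | f = 50% | f = 100% |
|---|---|---|---|
| 2 weeks | 0.08 | 0.15 | 0.30 |
| 4 weeks | 0.15 | 0.31 | 0.60 |
| 8 weeks | 0.32 | 0.63 | 1.22 |

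At m = 4.8 and 4 weeks the excesses are 0.16, 0.31 and 0.61.

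**Fewer early failures.** Replace S(L) by 1 − e, keep the constant-hazard slope around the median, and take f = 100%, m = 6.5. For e = 1%, 2% and 5% the pooled excess is 0.06, 0.12 and 0.31 months.

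**Simulation (1,500 runs, 225 + 125 patients, 4 weeks, f = 100%).**

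| True median | Ordinary Kaplan-Meier | Delayed-entry Kaplan-Meier |
|---|---|---|
| 6.5 | 7.09 | 6.51 |
| 4.8 | 5.38 | 4.80 |

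At 6.5 months the standard deviation of the median is 0.50 (ordinary) and 0.53 (delayed entry).

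**The case against.** **Late entry may be rare.** Protocol 8.1.1 and SAP 2.1 describe enrolment at treatment start. The quality-of-life baseline window closes on Day 1 (SAP Appendix A1.1), which fits that intention. A reader might infer from criterion 7 that early failures are in fact lost. The documents show only that they can be. This stands, and the wording here is conditional for that reason.

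**Few PFS events can occur this early.** SAP 6.1.1 counts progression from a tumour assessment at an axitinib follow-up visit, and scans are expected about every 2 months. Stopping axitinib for reasons other than progression is censored for PFS. Before the first visit, PFS events are therefore mainly deaths, and the constant-hazard figure of 9.3% is probably high. This stands for PFS, and the 1–5% rows are the more plausible ones. It does not protect TTF, where stopping for intolerability counts as an event and needs no scan.

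**The AXIS comparison is untouched.** A reader might infer that the threshold in Protocol 8.5, "at least 4.9 months" against 6.5, would be passed too easily. That comparison is assigned to the 125 patients enrolled at sunitinib start, whose axitinib PFS late axitinib enrolment cannot bias. SAP 4.2 also plans no statistical test.

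**Not every patient can be late.** In the axitinib pool alone, with all patients late by 4 weeks, a true 6.5 would read 7.42 (+0.92). A reader might take that as the error in the primary result. The primary analysis pools all 350, so the corresponding maximum is 7.10.

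**Delayed entry can itself lose events.** If progression or a stop is found at or just before the enrolling visit, the event falls at or before entry and would drop out, although the current analysis keeps it. This stands, and the fix must deal with it.

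**Conclusion.** The point holds as a possible upward bias in the pooled axitinib-line PFS and TTF medians. It arises only in the patients enrolled at axitinib start, and nothing in the SAP corrects it or would reveal it.

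Its size is unknown because the share enrolling late is unknown. For PFS with a 4-week first visit it runs from near zero to at most about 0.6 months under constant hazard, and to about 0.3 months if no more than 5% fail before entry. It is larger if first visits fall later. The constant-hazard maximum is slightly more than one sampling standard deviation of the median (about 0.5 months). TTF is probably more exposed, but the documents give no TTF median from which to size it.

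The point does not extend to the SU-AXI sequence endpoints. These are timed from first sunitinib dose in patients who must survive to start axitinib. That is a separate conditioning problem, and entry at inclusion would not repair it. This is a minor, inexpensive improvement and not a flaw that undermines the study.

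**What to change.** In SAP 8.1.2 and 8.2.2, for axitinib-line PFS and TTF only, including the Cox model for axitinib PFS:

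- Keep time from first axitinib dose. For patients enrolled at axitinib start, set risk-set entry at the CRF inclusion date if that is later than first dose. Patients enrolled at sunitinib start enter at time zero.
- State how a progression or stop found at the enrolling visit is counted, so that it is not dropped.
- Report the number included after first dose and the distribution of the delay in days.
- Show the standard Kaplan-Meier estimate alongside.
- Add late entry to the limitations in Protocol 8.9.

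The cost is one entry-time variable built from a date already collected. Early risk sets are slightly smaller (in the extreme simulated case the standard deviation of the median rises from 0.50 to 0.53 months), and the median may be slightly less favourable. Delayed entry also assumes that entry time is independent of prognosis, which should be stated. If late enrolment proves rare, the two estimates will nearly coincide and the reported delays will show why.

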8.3. Variables

Variable	Role	Data source(s)
Patient demographics (year of birth, gender, height, weight)	baseline characteristics	Initiation visit
Performance status (ECOG, Karnofsky)	baseline characteristics, potential confounder	Initiation visit Follow up visit
Risk groups (MSKCC risk, Heng risk)	baseline characteristics, potential confounder	Initiation visit
Comorbidities	baseline characteristics, potential confounder	Initiation visit
Lab tests (abnormal findings – levels when abnormal)	baseline characteristics, potential confounder	Initiation visit Follow up visit
Blood Pressure measurement (Y/N, date of exam and level, antihypertensive treatment)	baseline characteristics, outcome	Initiation visit Follow up visit
Electrocardiogram (Y/N/date of exam/ abnormal findings)	baseline characteristics,	Initiation visit
Echocardiography (Y/N/date of exam/ abnormal findings, LVEF)	baseline characteristics,	Initiation visit
Tumor history (date of first diagnosis, TNM, Grade at diagnosis /at enrolment, Histology)	baseline characteristics	Initiation visit
Metastasis (date of first detection and	baseline characteristics	Initiation visit

localisation)		
Previous treatments for RCC (Surgery, radiotherapy, other / for primary tumor/ for metastasis)	baseline characteristics, potential confounder	Initiation visit
Sunitinib therapy (starting date and dose, dose change, change of schedule)	exposure	Initiation visit Follow up visit
Axitinib therapy (starting date and dose, dose titration up, dose reduction, change of schedule)	exposure, effect modifier/sub-group identifier	Initiation visit Follow up visit
Additional anti tumor treatment (name and dose)	exposure, potential confounder	Inclusion visit Follow up visit
Comedications (name of products, starting and ending dates)	exposure, potential confounder	Initiation visit Follow up visit
Sunitinib / Axitinib Progression (Y/N and date)	outcome	Initiation visit Follow up visit
Sunitinib / Axitinib Tumor Response	outcome	Initiation visit Follow up visit
Sunitinib / Axitinib Safety : AE description and AE grade (according CTCAE)	outcome	Initiation visit Follow up visit
Sunitinib / Axitinib discontinuation	outcome	Follow up visit
Axitinib QoL (FKSI-19, and MH and RE domains of SF-36)	outcome	Initiation visit Follow up visit End of treatment
Death (Y/N,date, Cause)	outcome	Follow up visit

Table 1 : variables collected during study

Detailed definitions will be included in the Statistical Analysis Plan

